1.0 TRIAL SUMMARY

Abbreviated Title	Pembrolizumab (MK-3475) in uveal melanoma
Trial Phase	II
Clinical Indication	Advanced uveal melanoma
Trial Type	Two-stage, single arm trial
Type of control	None
Route of administration	Intravenous
Trial Blinding	None
Treatment Groups	Pembrolizumab 200mg every 3 weeks
Number of trial subjects	10-29
Maximum Duration of Therapy	24 months

1.1 SUMMARY OF RATIONALE

The programmed cell death 1 (PD-1) pathway represents a major immune control switch which may be engaged by tumor cells to overcome active T-cell immune surveillance (1). The ligands for PD-1 (PD-L1 and PD-L2) are constitutively expressed or can be induced in various tumors (2-5). High expression of PD-L1 on tumor cells (and to a lesser extent of PD-L2) has been found to correlate with poor prognosis and survival in various cancer types, including renal cell carcinoma (RCC) (6), pancreatic carcinoma (7), and ovarian carcinoma (8). Furthermore, PD-1 has been suggested to regulate tumor-specific T-cell expansion and function in patients with malignant melanoma (9, 10). Preclinical in vitro and in vivo experiments have shown that PD-1 and/or PD-L1 blockade using monoclonal antibodies (mAb) enhances tumor-cell specific T-cell activation, cytokine production, anti-tumor effector mechanisms, and clearance of tumor cells by the immune system (7, 9, 11-15).

Recent data with nivolumab (BMS-936558), an IgG4 antibody against PD-1, have validated PD-1 as an attractive target for clinical therapeutic intervention (16). In a recent report of the clinical trial data with nivolumab a total of 296 patients with advanced melanoma, non-small cell lung cancer (NSCLC), castration-resistant prostate cancer, renal-cell carcinoma or colorectal cancer were treated at a dose of 0.1, 0.3, 1, 3, or 10 mg/kg every 2 weeks. Among 236 evaluable patients, cumulative response rates (all doses and defined by the Response Evaluation Criteria in Solid Tumors [RECIST] were 18% among patients with NSCLC, 28% among patients with melanoma, and 27% among patients with renal-cell cancer. Responses were reported to be durable: 20 of 31 responses lasted 1 year or more in patients with 1 year or more of follow-up. Grade 3 or 4 adverse events were observed in 49% of patients, while 14% of patients had treatment related Grade 3 or 4 adverse events. Drug-related adverse events of special interest (e.g., those with potential immune-related causes) occurred in 41% of patients and included pneumonitis, vitiligo, colitis, hepatitis, hypophysitis, and thyroiditis (16).

Pembrolizumab (MK-3475, previously known as SCH 900475) is a potent and highly-selective humanized mAb of the IgG4/kappa isotype designed to directly block the interaction between PD-1 and its ligands, PD-L1 and PD-L2. Pembrolizumab strongly enhances T lymphocyte immune responses in cultured blood cells from healthy human donors, cancer patients, and primates. In T-cell activation assays using human donor blood cells, the EC50 was in the range of 0.1 to 0.3 nM. Pembrolizumab also modulates the level of interleukin-2 (IL-2), tumor necrosis factor alpha (TNF α), interferon gamma (IFN γ), and other cytokines. The antibody potentiates existing immune responses only in the presence of antigen and does not nonspecifically activate T-cells (for details see the Pembrolizumab Investigator's Brochure).

Despite the recent advances in the treatment of melanoma patients, overall outlook for patients with metastatic disease remains dismal and the development of new effective therapy is still needed. Particularly, the outlook for uveal melanoma remains especially grim. Anti-PD1 mAb nivolumab has reported a response rate of 28% in cutaneous melanoma patients (16). Pembrolizumab has shown a very promising early response rate of 42% in patients who have not received prior ipilimumab treatment, which is much higher than the 11 or 15% response rate observed in ipilimumab registration trials (17).

Uveal melanoma is an uncommon cancer occurring in 3000 patients per year in the United States. At the onset of advanced/metastatic disease, however, this condition has an especially poor prognosis without clearly effective treatment options. Preclinical rationale for use of pembrolizumab in this population is strong. Uveal melanoma cell lines express PD-L1, which predicts for response to therapy in cutaneous melanoma and in NSCLC (18). Uveal melanomas are heavily infiltrated with leukocytes, including CD8+ T cells, potentially indicating functional exhaustion of the immune response (19-21). Finally, although responses occur less frequently than in cutaneous melanoma, objective responses have been reported with ipilimumab in uveal melanoma (22, 23). Taken together, the existing data support the evaluation of the safety and efficacy of pembrolizumab in patients with uveal MEL for whom additional treatment options are needed.

1.2 SUMMARY OF TRIAL DESIGN

Patients will receive pembrolizumab at 200mg IV Q3W at a fixed dose. All patients with advanced uveal melanoma enrolled in the study will receive up to 24 months of pembrolizumab treatment until disease progression, unacceptable toxicity, the withdrawal of consent, confirmed complete response or they require another form of antineoplastic therapy as determined by the Investigator. In the event of a confirmed complete response (CR), it is at the discretion of the investigator to keep a patient on study treatment or to suspend study treatment based on the criteria outlined in section 5.2.3. Patients will continue to be monitored with scheduled disease assessments as described in the protocol (as if the patient were continuing on study treatment), and in the event of a disease recurrence, pembrolizumab may be resumed (Second Course treatment) upon disease recurrence in these patients. Second Course treatment with pembrolizumab may be given for up to 12 additional months. See Section 7.1.6.2 for details regarding second course treatment.

After receiving 24 months of treatment with pembrolizumab, patients with CR, PR or SD will no longer receive treatment with pembrolizumab and will complete the 30-Day Safety Follow Up visit and then proceed to the Post Treatment Follow up visits for up to an additional 48 months per the Flow Chart Section 6.1. At any point in the Post treatment follow up period, if a patient experiences disease progression they are eligible to receive the 12 month Second Course Treatment with pembrolizumab.

Patients who discontinue study treatment for reasons other than documented progression should continue to have CT imaging assessments per schedule as indicated in the Post-Treatment Discontinuation Follow-up per Section 6.0 of the Flow Chart. Patients will enter the survival follow-up phase after confirmed disease progression is documented.

2.0 TRIAL DESIGN

2.1 Trial Diagram

Figure 1: Study schema

2.2 Trial Design

2.2.1 Summary of Trial Design

This is an open-label, two stage, single arm pivotal study of intravenous (IV) pembrolizumab in patients with advanced or metastatic uveal melanoma. The primary endpoint of the study will be objective response rate (ORR). Other endpoints include progression-free survival (PFS), overall survival (OS), response duration, safety, and correlation of response rate with biomarkers (GNAQ/GNA11 mutational status, PD-L1 expression).

The study will enroll 10 patients in stage I of this two stage design; if one or more responses occur, an additional 19 patients will be enrolled. The sample size was designed to test whether pembrolizumab has a $\geq 20\%$ response rate in uveal melanoma with a clinically uninteresting response rate of 5%. In addition, if ≥ 2 patients experience stable disease (SD) for > 24 weeks, then the study may proceed to stage 2 if the sponsor and PIs are in agreement.

The primary objective of the study is to evaluate the activity of pembrolizumab in terms of ORR. The overall type I error rate for this study is strictly controlled at 5% (two-sided) and the study has a power of 80%. The study is considered to be positive if at least 4 patients treated with pembrolizumab have an objective response (of 29 subjects enrolled). All patients receiving pembrolizumab will receive pembrolizumab as IV infusion at a dose of 200mg every 3 weeks until disease progression, intolerable toxicity, confirmed complete response,

withdrawal of consent, or they require another form of antineoplastic therapy as determined by the Investigator.

We anticipate an accrual rate of 1 to 2 patients per month from 3 participating centers.

After the baseline tumor evaluation, tumor assessment during the study will be performed by radiological scans every 6 weeks starting from Week 12 until Week 24. At the discretion of investigators, patients who remain on study after 24 weeks and are clinically stable may decrease imaging frequency to every 12 weeks in the following schedule:

- First scheduled disease assessment: week 12
- Disease assessments every 6 weeks from week 18-24
- Disease assessments every 12 weeks from week 36-96

Patients will be evaluated for tumor response and patient management by sites based on the Immune Related RECIST [irRECIST] criteria (Section 7.1.3.3) by the investigator with site radiology reading. Guidelines for irRECIST as described in section 7.1.3.3. On-study assessments by irRECIST take into account the observation that some patients with melanoma can have a transient tumor flare in the first few months after start of immunotherapy with subsequent disease response. Clinical decisions will be based on the interpretation of the investigator at the site treating the patient in real time using the irRECIST criteria.

All patients must have at least one baseline measurable lesion by RECIST 1.1 definition on CT or MRI (as assessed by investigators) (24). The timing for tumor assessments should be based on the calendar and not adjusted for delays or variation in cycle starts.

Patients will be monitored regularly for safety and efficacy throughout the study, as per Section 6.0, Study Flow Chart. Fresh tumor tissue or archived tumor tissue is required for biomarker analysis prior to randomization, then optional at specific timepoints during the study (see Sections 6.1).

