strategy in uveal melanoma. Second, uveal melanoma cell lines demonstrate PD-L1 expression. In a group of metastasis cultures of uveal melanoma cell lines, nearly all lines demonstrated PD-L1 expression which was further augmented with interferon- γ stimulation (11). Although very few patients with uveal melanoma have been treated with anti-PD-1 therapies or have been assessed for PD-L1 expression, this suggests that the PD-1/PD-L1 axis may be a functionally relevant mechanism of immune evasion in uveal melanoma. Third, to evaluate the functional consequences of PD-1 blockade, uveal melanoma cell lines were grown in culture with CD3+ T cells (12). In IFN- γ stimulated cell lines, the addition of anti-PD-1 caused a T cell activation and significant increase in IL-2 production by the CD3+ T cells. Additionally, T-cell activation was found to be promoted by RNA interference of PD-L1 in a co-cultured uveal melanoma cell line with CD3+ T cells (13). Fourth, early phase studies have suggested that PD-L1 expression correlates with response to anti-PD-1/PD-L1, even in cancers other than melanoma, lung cancer, and renal cell carcinoma. (16, 47, 48). Based on cell line experiments, at least a subset of uveal melanomas would be predicted to express PD-L1, potentially predicting benefit from pembrolizumab. Finally, ipilimumab has demonstrated benefit in patients with uveal melanoma. In a retrospective review 39 patients with metastatic uveal melanoma were treated with ipilimumab. ORR by IrRC was 5.4% with one complete response and one partial response. An additional 28% of patients demonstrated stable disease at 23 weeks demonstrating that immune checkpoint inhibition may be an effective therapeutic strategy in uveal melanoma (16).

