5.10 Clinical Criteria for Early Trial Termination

Early trial termination will be the result of the criteria specified below:

1. Quality or quantity of data recording is inaccurate or incomplete
2. Poor adherence to protocol and regulatory requirements
3. Incidence or severity of adverse drug reaction in this or other studies indicates a potential health hazard to subjects
4. Plans to modify or discontinue the development of the study drug
5. Lack of efficacy as defined by no responses in the first 10 patients AND <2 patients with stable disease at 24 weeks.

In the event of Merck decision to no longer supply study drug, ample notification will be provided so that appropriate adjustments to subject treatment can be made.

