9.0 STATISTICAL ANALYSIS PLAN

9.1 Statistical Analysis Plan Summary

The primary objective is to determine whether pembrolizumab is an effective therapy in uveal melanoma. The null hypothesis is that the objective response rate (ORR; percentage of patients achieving a confirmed CR or PR) is not attractive (defined as $\leq 5\%$). The alternative hypothesis is that the response rate is of interest for further development (defined as $\geq 20\%$).

Product: MK-3475
Protocol/Amendment No. 03

The final analysis of the overall response rate will be performed with a power of 80% with one sided $\alpha=0.05$. It is calculated that at least 4 responses are needed out of a total of 29 patients to reject the null hypothesis.

To allow early termination of the trial due to lack of efficacy, the trial will be conducted in two stages per Simon's Optimal Design. If no responses are demonstrated in the first 10 patients, then the trial will be terminated early for futility. If ≥ 1 responses are observed, enrollment will continue to 29 patients. Notably, in the absence of ≥ 1 response, if ≥ 2 patients experience stable disease (SD) for >24 weeks, then the study may proceed to stage 2 if the sponsor and PIs are in agreement. This provision was added since the probability of early termination was as high as 10% even with a response rate of 20%.

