9.2 Statistical Analysis Plan

9.2.1 Sample Size Assumptions

To determine the overall sample size and the interim sample size, a two stage Simon's Optimal design was evaluated. To test the hypotheses (ORR=5% vs. 20%), 1 response from the first 10 subjects would be required to progress to stage 2 and a total of 29 subjects will be needed to achieve the desired type I ($<5\%$) and type II error rate (Power $>80\%$). The risk of prematurely stopping the trial after stage I if the drug is effective is approximately 10%. To reduce this risk, we will include the condition that if 2 or more patients experience stable disease for at least 24 weeks then the trial will proceed to stage 2.

Table 11: Sample Size Calculations

If the True Response Rate to pembrolizumab is: (%)	Probability of Early Termination after Stage I	Probability of Rejecting the Null Hypothesis
5%	0.599	0.047 (type 1 error)
10%	0.349	0.289
15%	0.197	0.589
20%	0.107	0.801
25%	0.056	0.913
30%	0.028	0.963

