9.2.2 Efficacy Endpoints

9.2.2.1 Primary Endpoint

Objective response rate (ORR) as defined by immune-related response criteria (irRC) will be the primary endpoint of the study. As mentioned, the primary hypothesis is that ORR of pembrolizumab in uveal melanoma will be 20%. We will enroll 10 patients in stage I to allow for early termination for futility. If no responses are observed the trial will be terminated. However, if ≥ 1 objective response occurs, OR if ≥ 2 patients experience stability of disease for ≥ 24 weeks, the trial will proceed to stage II.

Product: MK-3475

Protocol/Amendment No. 03

In stage II, an additional 19 patients will be enrolled. If ≥ 4 responses occur in all patients treated on stage I and stage II, the trial will be considered positive.

Of note, response rates by RECIST 1.1 criteria will also be assessed although irRC will be used for the primary endpoint.

ORR will be stratified by PD-L1 expression and *GNAQ/GNA11* mutation status (see section 8.2.2.3).

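### Section 2.2.1 claims a type I error strictly controlled at 5% two-sided, but the design is one-sided and its stop at 0/10 can be overridden, so the one-sided error lies between 0.047 and at most 0.055

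*Combined protocol and SAP*

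**What the plan says.** **Error rate.** Section 2.2.1 says: "The overall type I error rate for this study is strictly controlled at 5% (two-sided) and the study has a power of 80"%. Section 9.1 says: "The final analysis of the overall response rate will be performed with a power of 80% with one sided" alpha = 0.05. Both sections apply the same success rule, at least 4 responses among 29 patients. Section 9.2.1 names no side. Its Table 11 gives "0.047 (type 1 error") at a true response rate of 5%, a rejection probability of 0.801 at 20%, and early-termination probabilities of 0.599 and 0.107.

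**Continuing after 0/10.** All five relevant sections let the trial go on without a response if at least 2 patients have prolonged stable disease, but in different terms:

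| Section | Continuation after 0/10 with at least 2 stable patients | Stable-disease duration |
|---|---|---|
| 2.2.1 | discretionary | more than 24 weeks |
| 9.1 | discretionary: "then the study may proceed to stage 2 if the sponsor and PIs are in agreement" | more than 24 weeks |
| 9.2.1 | automatic: "if 2 or more patients experience stable disease for at least 24 weeks then the trial will proceed to stage 2" | at least 24 weeks |
| 9.2.2.1 | automatic: "24 weeks, the trial will proceed to stage II" | at least 24 weeks |
| 5.10 | not a ground for termination: "Lack of efficacy as defined by no responses in the first 10 patients AND <2 patients with stable disease at 24 weeks" | at 24 weeks |

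**The concern.** Two claims in the sentence in 2.2.1 do not fit the rest of the plan.

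First, one cutoff cannot be both a two-sided and a one-sided 5% test. By the usual reading, two-sided 5% leaves 0.025 in the upper tail, so a reader of the design summary would credit the trial with a stricter standard than the statistical section sets.

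Second, *strictly controlled* requires the stated error to hold under the rules the trial will follow. If Table 11 was computed with a stop at 0/10 that is always obeyed, the stable-disease route adds false positives that the table does not count. It also lowers the chance of stopping early for an inactive drug. The stated operating characteristics would then belong to a design slightly different from the one described.

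**Working it through.** **Inputs.** Null response rate 5%, alternative 20%; stage 1 n = 10, stage 2 n = 19; continue with at least 1 response; reject with at least 4 of 29 (sections 9.1, 9.2.1, 9.2.2.1). X₁ and X₂ are the stage 1 and stage 2 response counts.

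**Step 1: reproduce Table 11 with the stop at 0/10 always followed.**

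P(reject) = Σ over x = 1 to 10 of P(X₁ = x) × P(X₂ ≥ max(0, 4 − x)).

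At a 5% response rate:

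| Stage 1 responses | P(X₁ = x) | P(enough in stage 2) | Product |
|---|---|---|---|
| 1 | 0.31512 | 0.06655 | 0.02097 |
| 2 | 0.07463 | 0.24529 | 0.01831 |
| 3 | 0.01048 | 0.62265 | 0.00652 |
| 4 or more | 0.00103 | 1 | 0.00103 |
| Sum | | | 0.0468 |

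The same sum at 20% gives 0.8011. P(0 of 10) is 0.95¹⁰ = 0.5987 at 5% and 0.80¹⁰ = 0.1074 at 20%. These match Table 11 (0.047, 0.801, 0.599, 0.107), and the other four rows reproduce as well. Two things follow. The 0.047 is an upper-tail probability. And the early-termination column is exactly P(0 of 10), so both columns assume that every 0/10 outcome ends the trial.

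**Step 2: which side fits.** A search over two-stage designs for 5% versus 20% with 80% power returns 10/29 with at least 4 responses as the Simon optimal design at one-sided 0.05. Against 0.025, the rule's 0.0468 is too large. A cutoff of 5 of 29 would give 0.0124, but power of only 0.681.

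**Step 3: add the stable-disease route.** Let q be the share of 0/10 outcomes after which the trial continues. After 0/10, at least 4 of the 19 stage 2 patients must respond.

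- At 5%: P(at least 4 of 19) = 0.01324. Added error = 0.5987 × 0.01324 × q = 0.00792q.
- Error = 0.04683 + 0.00792q. At q = 1 this is 0.0548, which equals P(at least 4 of 29). No continuation rule after stage 1 can exceed it, because success always needs 4 of 29.
- Error = 0.05 at q = (0.05 − 0.04683) / 0.00792 = 0.40.
- At 20%: P(at least 4 of 19) = 0.5449, so power = 0.8011 + 0.1074 × 0.5449 × q = 0.8011 + 0.0585q, at most 0.860.

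**Step 4: what q might be.** The plan assumes no stable-disease rate. Suppose, as an assumption, that patients are independent, that a share s of all patients has qualifying stable disease, and that the provision is used whenever it is triggered. Among non-responders the rate is s / 0.95, and q = P(at least 2 of 10) at that rate. At a 5% response rate:

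| Assumed s | q | One-sided error | Early termination, 0.5987 × (1 − q) |
|---|---|---|---|
| 5% | 0.094 | 0.0476 | 0.54 |
| 10% | 0.284 | 0.0491 | 0.43 |
| 15% | 0.484 | 0.0507 | 0.31 |
| 20% | 0.655 | 0.0520 | 0.21 |
| 28% | 0.842 | 0.0535 | 0.09 |

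The error reaches 0.05 at s of about 12.8%. The 28% row borrows the ipilimumab figure in section 4.2.1, "An additional 28% of patients demonstrated stable disease at 23 weeks". It concerns another drug in a retrospective review and serves here only as an illustration.

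**The case against.** The best defence is that nothing in Table 11 is miscalculated and that section 9.1 states the correct side, so this is a labelling slip in a summary section. That is true of the arithmetic, but the summary still makes an incorrect claim.

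A second objection is that the futility stop is conditional rather than absent: with no responses and fewer than 2 stable patients, section 5.10 does end the trial. This stands. The 0.0548 is therefore a ceiling and not an expected value. With stable-disease rates of 5% or 10%, the error stays below 0.05 even if the provision is always used. Under the discretionary wording in 2.2.1 and 9.1, the sponsor and investigators could also decline every time, and Table 11 would then be exact. So Table 11 *may* overstate early stopping for an inactive drug; how far depends on a rate the plan does not give and on which wording governs. What does not survive is *strictly controlled*, since the rules permit an error above 5%.

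Third, the provision is disclosed, its purpose is explained (a risk of about 10% of stopping an effective drug), and it raises power. This also stands, and the corrected text should report the gain in power alongside the rise in error.

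**Conclusion.** The concern holds, as a minor point. The two-sided label in 2.2.1 is wrong for the 4-of-29 rule: the upper-tail error is 0.0468 with the stop followed, against the 0.025 that two-sided 5% usually implies. *Strictly controlled* is unsupported, because the stable-disease route lets the one-sided error lie anywhere from 0.0468 to 0.0548, with power at 20% from 0.801 to 0.860.

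These bounds need only exact binomial counts and the stated cutoff. Where the error falls between them depends on an unstated stable-disease rate and on whether continuation is automatic. The excess over one-sided 5% is at most 0.5 percentage points. The possible effect on early stopping for an inactive drug is larger, from 0.599 down to 0.09 in the 28% illustration. The sample size, the cutoff and the existence of the provision are not in question.

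**What to change.** Replace the sentence in 2.2.1 with wording such as:

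> The one-sided type I error is 4.7% and the power is 80% if enrollment stops after 0 responses in 10 patients. Because the stable-disease provision allows stage 2 after 0/10, the one-sided error may be as high as 5.5% and the power as high as 86%.

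Add a note under Table 11 that both columns assume the stop at 0/10 is always followed, and repeat the bounds there. Choose one form of the continuation rule, automatic or discretionary, with one stable-disease duration, and use it in sections 2.2.1, 5.10, 9.1, 9.2.1 and 9.2.2.1.

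The cost is one sentence, one table note and consistent wording in five places. It needs no extra patients and no new cutoff. The only downside is a slightly less favourable stated error.
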